7.1. Study Patients

7.1.1. Disposition of Patients

A table summarizing the number of screened patients, number and percentage of screen failures, number and percentage of randomized patients among all screened patients and number of patients treated with ravulizumab among those randomized to ravulizumab + BSC will be provided. By-patient listing of the reasons for screen failure will also be produced.

Summaries and by-patient listings of patient disposition will include all patients randomized in the study. The following summaries will be generated:

- Patients who were randomized

- In the study
- By region (United States, Europe, Asia)
- By country
- By site
- Patients who completed the study
- Patients who discontinued the study with reason for discontinuation
- Patients in the analysis datasets and reason for exclusion from specific datasets
- Patients with inclusion/exclusion criteria violations

7.1.2. Protocol Deviations

Protocol deviations will be summarized in a tabular format and listing.

For the purposes of defining the PPS, important protocol deviations are:

- Not meeting all of the key inclusion/exclusion criteria.

Key inclusion criteria are:

- Confirmed diagnosis of SARS-CoV-2 infection (eg, via polymerase chain reaction [PCR] and/or antibody test) presenting as severe COVID-19 requiring hospitalization.
- Severe pneumonia, acute lung injury, or ARDS confirmed by computed tomography or x-ray at Screening or within the 3 days prior to Screening, as part of the patient's routine clinical care.
- Respiratory distress requiring mechanical ventilation, which can be either invasive (requiring endotracheal intubation) or noninvasive (with continuous positive airway pressure [CPAP] or bilevel positive airway pressure [BiPAP]).

Key exclusion criteria are:

- Patient is not expected to survive for more than 24 hours.
- Patient is on invasive mechanical ventilation with intubation for more than 48 hours prior to Screening.
- Severe pre-existing cardiac disease (ie, New York Heart Association Class 3 or Class 4, acute coronary syndrome or persistent ventricular tachyarrhythmias).
- Patients who took less than 100% of the required treatment doses while alive and in the ICU.

7.1.3. Demographics, Disease Characteristics, and Medical History

Patient demographic and baseline disease characteristics will be summarized by treatment group and randomization stratification factor using the ITT population and the PPS. Summary statistics will be presented. No formal hypothesis testing will be performed. By-patient listings will be produced.

7.1.3.1. Demographics

The following demographic variables will be summarized:

- Age (at first dose date in years)
- Sex
- Race and ethnicity
- Region and country
- Baseline weight (kg)

7.1.3.2. Disease Characteristics

The following disease characteristics will be summarized:

- Number (percentage) of patients with a positive SARS-CoV-2 test
- Number (percentage) of patients hospitalized
- Number of days from onset of signs and symptoms to hospitalization and to Day 1
- Number of days from hospitalization to Day 1
- Number (percentage) of patients in the ICU
- Number of days from first ICU date to Day 1
- Oxygen saturation level (SpO₂), PaO₂ from arterial blood gas, amount of supplemental oxygen (FiO₂) received, SpO₂/FiO₂ and PaO₂/FiO₂ at baseline
- Number (percentage) of patients on respiratory support and method of support on Day 1
- SOFA score at baseline
- Number (percentage) patients by smoking status

7.1.3.3. Medical History and Baseline Physical Examination

Medical histories will be coded by primary System Organ Class (SOC) and Preferred Term (PT) using the Medical Dictionary for Regulatory Activities (MedDRA) (version 23.0 or higher). Baseline medical history information, ie, number (percentage) of patients who have a medical history, will be summarized by SOC and PT for the ITT population and by the randomization stratification factor. Baseline physical examination information will also be summarized for the ITT population. By-patient listings will be created for medical history and physical examinations.

7.1.4. Prior and Concomitant Medications or Therapies

Prior medications or therapies are defined as medications taken or therapies received by patients prior to Day 1 in the study. Concomitant medications or therapies are defined as medications taken or therapies received by patients during the study on or after Day 1. Medications will be coded using the World Health Organization Drug Dictionary (WHO DD Mar 2018 or higher). Therapies will be coded using MedDRA (version 23.0 or higher). Summaries will be performed

on the ITT population. The number (percentage) of patients using prior and concomitant medications will be summarized based on the World Health Organization Anatomical Therapeutic Chemical (WHO ATC) Level 4 Class code and generic name. The number (percentage) of patients using prior and concomitant therapies will be summarized by SOC and PT.

Prior and concomitant medications will be summarized overall and by potential subgroups of medications (eg, antivirals, immunomodulators, steroids, hydroxychloroquine/chloroquine, convalescent plasma) depending on the distribution of medications used by patients in the study. By-patient listings of all reported medications will be produced.

If prohibited medications are used by patients in this study, then a listing of those patients and the respective prohibited medication(s) will be produced.

7.2. Efficacy Analyses

Efficacy analyses will be performed on the ITT population and the PPS will be used for sensitivity analyses. Baseline is defined as the last available assessment on or before Day 1 for all patients. By-patient listings of all efficacy data will be produced.

7.2.1. Primary Analysis

The primary efficacy endpoint is survival (based on all-cause mortality) at Day 29 and will be compared between the 2 treatment groups using a one-sided Mantel-Haenszel (MH) test of the difference in two proportions stratified by intubated or not intubated on Day 1 and a family-wise Type I error of 0.025. The estimated MH risk difference will be summarized along with the 2-sided 95% confidence interval (CI) using Mantel-Haenszel stratum weights ([Mantel, 1959](#)) and the Sato variance estimator. Handling of missing data for the primary analysis is described in [Section 7.2.1.1](#).

Survival will also be analyzed using the method of Kaplan and Meier (KM) and compared using a log-rank test stratified by intubated or not intubated on Day 1 as a sensitivity analysis. Hazard ratio and risk reduction will be summarized from a Cox proportional hazards model stratified by intubated or not intubated on Day 1. Confidence intervals (95%) will be presented for the survival estimate at Day 29 based on the complementary log-log transformation. Kaplan-Meier curves for both treatment groups will be produced.

A sensitivity analysis of the primary endpoint will also be performed using a 3-level categorical outcome of 3 (alive and discharged from the ICU); 2 (alive and in the ICU); or 1 (death). The 2 treatment groups will be compared using a proportional odds model with covariates for treatment group and the randomization stratification factor. If the assumption of proportional odds is rejected, a different approach will be considered.

Additional sensitivity analyses will include:

- A logistic regression with covariates for treatment group, age, sex, region, and randomization stratification factor. The estimate of the difference in survival proportions will be based on this logistic regression ([Ge, 2011](#)).

- A Cox proportional hazards model with covariates for treatment group, age, sex, region, and randomization stratification factor. The treatment group hazard ratio and risk reduction from the model will be summarized.

A summary table and listing of patients who died during the study will also be provided with reason for death, where available.

An interim analysis of the primary endpoint will also be conducted as described in [Section 7.4](#).

7.2.1.1. Handling of Dropouts or Missing Data

Missing survival data for the primary analysis will be imputed using a multiple imputation approach assuming the data are missing at random (MAR) and using a logistic regression model with covariates for treatment group, the randomization stratification factor, age, sex and presence of a pre-existing condition at baseline (diabetes mellitus, obesity, respiratory condition, and/or coronary artery disease). Sensitivity analyses will include:

- Worst-case scenario: missing survival data for patients randomized to ravulizumab + BSC group are imputed as death and missing survival data for patients randomized to BSC alone group are imputed as survived
- All available data: no imputation of missing data
- Best-case scenario: missing survival data for patients randomized to ravulizumab + BSC group are imputed as survived and missing survival data for patients randomized to BSC alone group are imputed as death
- Assuming death: all missing survival data is imputed as a death
- Assuming survival: all missing survival data is imputed as survived
- Delta-adjustment tipping point analysis ([O’Kelly and Ratitch, 2014](#)): this approach assumes that patients randomized to the ravulizumab + BSC group with missing survival data experience less survival, defined by an adjustment (delta), compared to patients with observed survival in the ravulizumab + BSC group; missing values for patients randomized to ravulizumab + BSC group are imputed by shifting the survival probability of the observed patients downward by delta until any positive conclusion drawn from the primary analysis is reversed; refer to [Appendix 9.5.2.1](#) for additional details

In another sensitivity analysis of the primary endpoint (ie, time to event), the patients who survive will be censored and will have a censor time that is based on the patient’s time from Day1 to the end of the Analysis Period, as described in [Appendix 9.5.1](#). A censoring indicator will be equal to 1 if the patient survived (was censored), and 0 if the patient died.

For the other sensitivity analyses of the primary endpoint (3-level categorical outcome and logistic regression model), missing data will be imputed using a multiple imputation approach assuming the data are missing at random (MAR) and using a logistic regression model with covariates for treatment group, the randomization stratification factor, age, sex and presence of a pre-existing condition at baseline (diabetes mellitus, obesity, respiratory condition, and/or coronary artery disease).

Missing data for the primary analysis of secondary endpoints will be handled as described in the secondary analyses in [Section 7.2.2](#).

7.2.1.2. Subgroup Analysis

A summary of survival at Day 29 will be produced by the following subgroups:

- Randomization stratification factor: intubated, not intubated
- Age group: <50 years, 50 to <70 years, ≥ 70 years
- Sex: Male, Female
- Region: United States, Europe, Asia
- Race: Asian, Black or African American, White, Other
- Ethnicity: Hispanic/Latino/Spanish origin, Not of Hispanic/Latino/Spanish origin
- Smoking status: Current/Former, Never
- Subgroups based on anticipated pre-existing conditions at baseline. Additional subgroups may be summarized depending on the distribution of medical histories of the patients in the study
 - Hypertension
 - Diabetes mellitus
 - Obesity
 - Respiratory conditions (eg asthma, COPD, pulmonary fibrosis/hypertension)
 - Coronary artery disease
- Subgroups based on anticipated concomitant medications used as BSC. Additional subgroups may be summarized depending on the distribution of medications used by patients during the study.
 - Use of any antivirals
 - Use of any immunomodulators
 - Use of any steroids
 - Use of any hydroxychloroquine/chloroquine
 - Use of any convalescent plasma

For each subgroup, the following descriptive summaries of survival will be produced:

- Summary of the number of patients
- Summary of the number (percentage) of patients with survival at Day 29
- Estimated risk difference between the 2 treatment groups along with a 95% CI
- Two-sided p-value from a stratified test of the difference in 2 proportions (if the sample size within a subgroup is too small, an unstratified test will be used)

- Hazard ratio and 95% CI from a Cox proportional hazards model with treatment covariate

If the use of concomitant medications is imbalanced by treatment group, the patients randomized to the ravulizumab + BSC group as a whole may be compared to subgroups of the BSC alone group with certain medication use (eg, antivirals, immunomodulators, hydrochloroquine/chloroquine).

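### BSC-drug survival subgroups are defined by use on or after Day 1, so unequal prescribing between open-label arms can bias their treatment-effect estimates in either direction

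*SAP*

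**What the plan says.** SAP 7.2.1.2 lists subgroups for Day 29 survival. Most are baseline characteristics, and the pre-existing conditions are expressly tied to baseline. The drug rows are not. They are "Subgroups based on anticipated concomitant medications used as BSC", each worded as use of any drug in a class, and the list may grow: "Additional subgroups may be summarized depending on the distribution of medications used by patients during the study".

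The time window comes from SAP 7.1.4: "Concomitant medications or therapies are defined as medications taken or therapies received by patients during the study on or after Day 1". The same section keeps a separate class, "Prior medications or therapies are defined as medications taken or therapies received by patients prior to Day 1 in the study", which 7.2.1.2 does not use for these rows. No baseline restriction, landmark time or time-dependent coding is given.

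Every subgroup receives an estimated risk difference with 95% CI, a "Two-sided p-value from a stratified test of the difference in 2 proportions", and a Cox hazard ratio. The introduction to these outputs reads "For each subgroup, the following descriptive summaries of survival will be produced". The closed testing procedure in SAP 7.2.2 covers only the primary endpoint and the five ranked Day 29 secondary endpoints.

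The section also contains a clause beginning "If the use of concomitant medications is imbalanced by treatment group". It allows the whole ravulizumab arm to be compared with "subgroups of the BSC alone group with certain medication use". That optional comparison is a separate matter. Here it matters only because it shows that unequal use was foreseen.

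**The concern.** Membership is fixed by events during the follow-up in which survival is counted. Someone who dies before a drug would have been started cannot become a user of it. Someone who deteriorates may be given it because of the deterioration. Randomisation does not protect a comparison within groups formed this way.

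The trial is open-label, and BSC follows local practice in both arms (protocol 4.1 and 6.3), so prescribing after Day 1 can depend on the known assignment. If it does, the patients selected into a row differ between arms, and the row can show a treatment effect when there is none.

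The comparator is BSC, so readers will look to these rows to see whether any ravulizumab effect holds alongside steroids, antivirals or immunomodulators. A false difference there could mislead on that question.

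**Working it through.** **The plan's own figures.** The SAP gives no number for these rows. The design figures serve as a yardstick: 60% versus 80% survival, 243 patients, 270 randomised (SAP 9.3). A fixed-design calculation (1-sided 0.025, pooled variance, 2:1) gives 240 in total; 162 + 81 gives 90.4% power; 243/0.9 = 270. The design effect is therefore 20 points.

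**Null model.** From the documents: 60% survival, deaths counted to Day 29 (SAP 9.5.1), 180 and 90 patients. Assumed: no effect of ravulizumab or of the BSC drug, 60% survival in both arms, constant hazards, nobody on the drug at Day 1, and start rates that the documents do not give.

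- Death hazard d = -ln(0.6)/29 = 0.01761 per day.
- Start hazard h = -ln(1 - p)/14, where p is the proportion who would start by Day 14 in the absence of death.
- Alive at Day 29 and never started: e = exp(-29(h + d)).
- Users: U = [h/(h + d)](1 - e).
- Survival in users = (0.6 - e)/U; in non-users = e/(1 - U).

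Ravulizumab, p = 30%: h = 0.02548, e = 0.2866, U = 0.422. Users 0.3134/0.422 = 74.3%; non-users 0.2866/0.578 = 49.6%.

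BSC, p = 50%: h = 0.04951, e = 0.1428, U = 0.632. Users 0.4572/0.632 = 72.3%; non-users 0.1428/0.368 = 38.8%.

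Rejection rates are 2-sided at 5%, from 10,000 simulated trials with an unstratified pooled Z-test:

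| Started by Day 14, ravulizumab vs BSC | User difference (rejection) | Non-user difference (rejection) |
|---|---|---|
| 50% vs 50% | 0.0 points (5%) | 0.0 points (5%) |
| 30% vs 50% | +2.0 points (5.6%) | +10.7 points (19%) |
| 20% vs 60% | +4.0 points (8%) | +21.9 points (53%) |
| 50% vs 30% | -2.0 points | -10.7 points |

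**Some patients already on the drug.** With 30% on the drug at Day 1 in both arms, the non-user differences stay at +10.7 and +21.9 points (rejection 14% and 41%, because the rows are smaller). The user differences fall to -0.2 and -0.8 points.

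**More extreme rates.** Constant daily start hazards over 28 days, with d = -ln(0.6)/28 and nobody on the drug at Day 1:

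- 0.05 vs 0.10: non-users 39.4% vs 19.7% (+20 points), users 72.4% vs 69.2% (+3).
- 0.03 vs 0.10: non-users 48.0% vs 19.7% (+28 points), users 74.0% vs 69.2% (+4.8).

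These imply that 62% or 46% of ravulizumab patients start, against 81% of BSC patients. About 17 of the 90 BSC patients remain as non-users.

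**Use driven by severity.** Suppose half the patients have 40% survival and half 80%, the same in both arms. Use in severe/milder patients is 60%/20% on ravulizumab and 80%/60% on BSC.

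- Ravulizumab users: (0.5×0.6×0.4 + 0.5×0.2×0.8)/(0.30 + 0.10) = 0.20/0.40 = 50.0%.
- BSC users: (0.5×0.8×0.4 + 0.5×0.6×0.8)/(0.40 + 0.30) = 0.40/0.70 = 57.1%.
- False difference: -7.1 points.

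**Checks.** In the simulations the overall ITT comparison has mean difference 0.00 and rejects about 5% of the time. With subgroups defined by baseline use, the mean false difference is within ±0.002 and rejection is 4.6% to 5.4%.

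**The case against.** The strongest reply is that these are descriptive rows outside the testing hierarchy. That is true, and it limits the consequence. But the label deals with how much inferential weight a result carries. It does not remove a bias in the estimate, and a p-value and hazard ratio are still printed.

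A reader might infer more: that the plan sets up user and non-user rows, that early deaths collect among non-users, and that ravulizumab therefore gains a false benefit of 20 to 28 points. The documents do not support that reading.

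- **Non-user rows are not listed.** For stratum, sex and smoking status the SAP writes out the levels. For drugs it names only use. The complement is the natural counterpart, but it is an inference, and the largest figures come from it.
- **Not every user had to survive to start.** The window includes drugs already running on Day 1, and enrolled patients are already hospitalised and ventilated. Those patients carry no survival-time bias.
- **Unequal use is required.** With no true effect and equal use in both arms, the timing mechanism distorts survival levels but not the difference between arms.
- **No direction is given.** Nothing says BSC-alone patients will receive other agents sooner. Reversing the rates reverses the sign.
- **The 20-point and larger figures need strong imbalance.** All start rates are assumptions.

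These points narrow the size and certainty of the problem. They leave the definition itself unanswered.

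**Conclusion.** The concern holds in limited form. The BSC-drug subgroups are formed after randomisation in an open-label trial, and their planned risk differences, p-values and hazard ratios can be biased in either direction if prescribing differs by arm.

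For the rows the SAP names, the false shift was modest in the cases tried: -7 points when use follows severity, +4 at 20% versus 60% started by Day 14, and nearly +5 at the most extreme rates. For complementary non-user rows, if produced, it was about 11 points at 30% versus 50% and reached or exceeded the 20-point design effect under stronger imbalance. All of this rests on assumed start rates, constant hazards and an inert BSC drug. The principle is secure; the size and direction in this trial cannot be known from the documents.

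The primary ITT analysis is not affected. This should be corrected, but it does not threaten the main result.

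**What to change.** In SAP 7.2.1.2, define each BSC-drug subgroup, including any added later, by use ongoing at randomisation. Protocol 6.5 already requires relevant drugs being received at enrolment to be recorded with start and end dates. Drugs stopped before enrolment are not clearly captured, so ongoing use is a safer definition than any earlier use.

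State a rule for incomplete dates. SAP 9.4.8 sets a missing start day to the first of the month, which could turn a drug begun after randomisation in that month into baseline use. For these subgroups, a start date that cannot be placed relative to randomisation should not count as baseline use by default. The rule should also say how a start on the day of randomisation is classed, because protocol 6.5 asks for dates and not times.

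Report drugs started later only as counts by arm with day of start, without treatment-effect estimates or p-values. Do not offer a Cox model with the drug as a time-varying covariate as an adjusted effect: it again conditions on something that assignment and severity can influence.

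The cost is SAP wording, one derivation and the date rule, with no new data collection. The downside is smaller user groups for drugs usually started after randomisation.

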### **9.4.1. Efficacy Analyses**

#### **9.4.1.1. Analyses of Primary Efficacy Endpoint**

The primary efficacy endpoint is survival (based on all-cause mortality) at Day 29 and will be compared between the 2 treatment groups using a 1-sided Mantel-Haenszel (MH) test of the difference in 2 proportions stratified by intubated or not intubated on Day 1 and a Type I error of 0.025. The estimated MH risk difference will be summarized along with the 95% confidence interval using Mantel-Haenszel stratum weights (Mantel, 1959) and the Sato variance estimator (Sato, 1989). Missing survival data for the primary analysis will be imputed using a multiple imputation approach assuming the data are missing at random (MAR) using a logistic regression model with covariates for treatment group, the randomization stratification factor, age, sex, and presence of a pre-existing condition at baseline. Sensitivity analyses will include the worst-case, all available, and best-case scenarios.

Survival will also be analyzed using the method of Kaplan and Meier (KM) and compared using a log-rank test stratified by intubated or not intubated on Day 1 as a sensitivity analysis. Hazard ratio and risk reduction will be summarized from a Cox proportional hazards model stratified by intubated or not intubated on Day 1. Confidence intervals (95%) will be presented for the survival estimate at Day 29 based on the complementary log-log transformation. Kaplan-Meier curves for both treatment groups will be produced.

A sensitivity analysis of the primary endpoint will also be performed using a 3-level categorical outcome of 3) alive and discharged from the ICU; 2) alive and in the ICU or 1) death. The 2 treatment groups will be compared using an ordinal logistic regression with covariates for treatment group and the randomization stratification factor.

Additional sensitivity analyses will include statistical models adjusting for age, randomization stratification factor, and other important baseline covariates. Subgroup analyses will also be performed by age group, randomization stratification factor, and other important baseline covariates. The Statistical Analysis Plan (SAP) will describe the sensitivity and subgroup analyses in greater detail.

An interim analysis of the primary endpoint will also be conducted as described in Section 9.5.

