7.2.1.4. Hypothesis Testing and Significance Level

All hypothesis testing other than for the primary analysis will be 2-sided and performed at the 0.05 level of significance. All estimates of efficacy parameters will be accompanied by 2-sided 95% CIs.

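### Seventeen survival subgroup factors get treatment p-values within levels, but no factor gets a test of whether the effect differs between its levels

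*SAP*

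**What the plan says.** Protocol 9.4.1.1 announces the subgroups and leaves the detail to the SAP: "Subgroup analyses will also be performed by age group, randomization stratification factor, and other important baseline covariates".

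SAP 7.2.1.2 then lists 17 factors:
- Seven have written levels: intubation stratum, age group, sex, region, race, ethnicity and smoking status. An example is "Race: Asian, Black or African American, White, Other".
- Five are conditions, under "Subgroups based on anticipated pre-existing conditions at baseline". Their levels are not written out.
- Five are medication classes, under "Subgroups based on anticipated concomitant medications used as BSC". Their levels are not written out either.

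The SAP allows further condition and medication subgroups once the distributions are known.

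The outputs are introduced with "For each subgroup, the following descriptive summaries of survival will be produced". They are the number of patients, the number and percentage surviving, "Estimated risk difference between the 2 treatment groups along with a 95% CI", a "Two-sided p-value from a stratified test of the difference in 2 proportions", and a hazard ratio with 95% CI. SAP 7.2.1.4 sets the general threshold: "All hypothesis testing other than for the primary analysis will be 2-sided and performed at the 0.05 level of significance".

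The only interaction term in either document is study day by treatment, in the repeated-measures models for SOFA and SpO2/FiO2 (Protocol 9.4.1.2; SAP 7.2.2.3 and 7.2.2.4). There is no treatment-by-subgroup test, no multiplicity statement for subgroups and no caution on reading the subgroup p-values.

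**The concern.** A subgroup table is read to see whether the treatment works better in some patients than in others. The p-value inside a level answers another question: whether the effect in that level alone can be told apart from zero. With one common effect, a large level will tend to reach 0.05 and a small one will not. A pair of levels with p = 0.01 and p = 0.30 is therefore weak evidence of a different effect, yet it is easily read as such.

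At stake is what the report seems to say about who benefits, for example intubated against non-intubated patients. The primary test, its alpha and the closed testing sequence are untouched.

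**Working it through.** **1. The plan's own figure.** Inputs from SAP 9.3: survival 60% v 80%, 81 v 162 patients, one-sided 0.025, pooled variance.
- Pooled survival = (0.6×81 + 0.8×162)/243 = 0.733.
- SE under no effect = √[0.733×0.267×(1/81 + 1/162)] = 0.0602.
- SE under the alternative = √[0.24/81 + 0.16/162] = 0.0629.
- Power = Φ[(0.20 − 1.96×0.0602)/0.0629] = Φ(1.305) = 0.904.

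This agrees with the stated power of at least 90% for a fixed design. With the interim look included, power is about 0.91.

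**2. Number of levels.** The seven written factors give 2+3+2+3+4+2+2 = 18. The other ten items add 10 if only the yes group is shown (28) or 20 if shown as yes/no (38).

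**3. Power inside a level when every patient has the same 80% v 60% effect.** Both SEs are divided by the square root of the level's share of the trial. The test is two-sided at 0.05.

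| Share of trial | Power, 243 patients | Power, 270 patients |
|---|---|---|
| 1/10 | 19% | 21% |
| 1/4 | 39% | 42% |
| 1/3 | 48% | 52% |
| 1/2 | 65% | 69% |
| 4/5 | 83% | 87% |

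The effect is identical in every row; only the size of the level changes.

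**4. Split verdicts (one level of a factor significant, another not), 243 patients.** Levels of one factor share no patients, so their results are taken as independent.
- Two equal halves: 2×0.646×0.354 = 46%.
- A 1/5 and 4/5 split: 0.325×0.166 + 0.675×0.834 = 62%.
- Three equal thirds: 1 − 0.484³ − 0.516³ = 75%.
- Four equal quarters: 1 − 0.388⁴ − 0.612⁴ = 84%.

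With equal-sized levels and all 38 shown, the expected count is 14×0.458 + 2×0.749 + 0.837 = 8.7 of 17 factors. Simulation of 1,500 trials of 243 patients, with independent factors, gave 8.7 for balanced levels and 10.0 for an uneven set of assumed prevalences. Reruns with equal-sized factors gave 8.3 to 8.6. At least one factor split in 98% to 99% of trials.

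If only the yes group is shown for the ten items, only the seven written factors can split on the page. The expected count is then 4×0.458 + 2×0.749 + 0.837 = 4.2 of 7.

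**5. The same simulated trials with one heterogeneity test per factor.** The statistic is Q = Σ wₖ(dₖ − d̄)², where dₖ is the risk difference in level k and wₖ its inverse variance, referred to χ² on (levels − 1) degrees of freedom. It flagged 0.94 to 0.98 of 17 factors on average, or 5.5% to 5.8% each.

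**6. Limits of the interaction test.**
- False flags among 12 baseline factors: 1 − 0.95¹² = 46% at exactly 5% each. At the simulated rates, 1 − 0.9446¹² = 49% and 1 − 0.9421¹² = 51%. Call it about 50%.
- Precision with two equal halves: the SE of one risk difference is √(0.24/40.5 + 0.16/81) = 0.089. The SE of their difference is 0.089×√2 = 0.126, so the 95% CI is about ±25 percentage points. That is wider than the 20-point effect the trial was sized for.

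**The case against.** **The table is descriptive.** The p-value is one of five items, beside two effect estimates with CIs. No rule makes a subgroup positive or negative, and subgroups lie outside the closed testing procedure. This stands. A reader might infer that the SAP will judge each subgroup at 0.05 and declare where ravulizumab works; no such rule is written. The label still does not make the p-value informative about differences between levels. SAP 7.2.1.4 supplies a 0.05 threshold without exempting subgroups.

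**The count of 38 is an inference.** This stands. The text fixes 18 levels and supports 28 to 38.

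**The remedy does not stop false positives.** A reader might infer that interaction tests would remove the risk of a chance finding if the drug does nothing. They would not. With no effect anywhere, at least one significant level among 38 appears in about 64% of simulated trials, and at least one significant interaction among 17 factors in about 62%. The gain lies in asking the right question, and in about 1 misleading factor instead of 8 to 10.

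**Deleting p-values is cosmetic while the CIs remain.** Largely true, because a 95% CI that excludes zero is nearly the same event as p below 0.05. The interaction test does the work.

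**Interaction tests do not suit every factor.** This stands for the five medication classes. SAP 7.1.4 counts a medication as concomitant if taken on or after Day 1. Membership can therefore follow from events after randomization, in an open-label trial.

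**The logistic model already planned could carry the interactions.** Only in part. The model in SAP 7.2.1 holds four of the 17 factors, and it tests a constant odds ratio. That is a different hypothesis from a constant risk difference.

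**Conclusion.** The point holds as a gap in the subgroup analysis. The plan reports p-values that do not address whether the effect differs between levels, and nothing in either document does address it. Under a uniform 80% v 60% effect, about 8 to 10 of 17 factors would show a split verdict, against about 1 of 17 flagged by a heterogeneity test.

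These figures assume:
- both levels of the ten condition and medication items are shown (otherwise about 4 of 7 factors with equal-sized levels);
- assumed level sizes, since the documents give no prevalences;
- an unstratified pooled Z-test in place of the stratified test, and no modelling of the interim look;
- factors simulated as independent. The average count does not depend on this, but the 98% to 99% chance of at least one split does.

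The consequence is for interpretation of a descriptive table. The documents do not support saying that any trial decision rests on these p-values.

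**What to change.** In SAP 7.2.1.2:

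1. For the 12 baseline factors (the seven with written levels and the five conditions), add one prespecified interaction test, or an interaction estimate with 95% CI, per factor. Use homogeneity of the risk difference across levels, to match the primary estimate.
2. Drop the within-level p-values or mark them as not for inference. Keep the number of patients, survival percentage, risk difference and 95% CI.
3. State that the interaction tests are exploratory, low-powered and unadjusted, with about a 50% chance of at least one false flag among 12 independent factors.
4. Keep the five on-study medication subgroups purely descriptive, with neither p-values nor interaction tests, and say why.
5. State whether the condition and medication items are shown as yes only or yes/no.

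The cost is a few lines of SAP text and one short calculation per factor. No new data are needed.
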